✓Compare

Institutional Review Board for Baylor College of Medicine and Affiliated Hospitals

Protocol Number: H-45486

Status: Closed

Initial Submit Date: 4/2/2019

Section Aa: Title & PI

A1. Main Title

EFFECT OF OPIOIDS ON VENTILATION IN CHILDREN WITH OBSTRUCTIVE SLEEP APNEA

A2. Principal Investigator

Name: [name]

[contact]

Id: 195273

Fax:

Department: ANESTHESIOLOGY: BCM

Email: [contact]

Center:

Mail Stn: BCM320

A3. Administrative Contact

Name: [name]

[contact]

Id: 160158

Fax:

Department: ANESTHESIOLOGY: BCM

Email: [contact]

Center:

Mail Stn: BCM320

Section Ab: General Information

A4. Co-Investigators

Name: [name]

[contact]

Id: 195204

Fax:

Department: ANESTHESIOLOGY: BCM

Email: [contact]

Center:

Mail Stn: BCM320

A5. Funding Source:

Baylor College of Medicine (Internal Funding Only)

A6a. Institution(s) where work will be performed:

TCH: Texas Children's Hospital

A6b. Research conducted outside of the United States:

Country:

Facility/Institution:

Contact/Investigator:

Phone Number:

If documentation of assurances has not been sent to the Office of Research, please explain:

A7. Research Category:

A8. Therapeutic Intent

Does this trial have therapeutic intent?

Not set yet

A9. ClinicalTrials.gov Registration

Section B: Exempt Request

B. Exempt From IRB Review

Not Applicable

Section C: Background Information

Ventilatory suppression in children following opioid administration is of obvious concern, especially following routine surgical procedures (i.e. adenotonsillectomy). It is thought that patients with obstructive sleep apnea (OSA) have increased sensitivity to opioids, especially in opioid naïve patients. Recent evidence in adults suggests that patients with moderate to severe OSA may not predispose patients to increased opioid sensitivity in the form of respiratory depression when compared with patients that do not have OSA. It is well known that OSA in children is significantly different from OSA in adults (e.g. gender predilection, central vs. peripheral causation). The manifestation and etiologies are very different in pediatric OSA making it a vastly different disease process. The aim of this study is to identify if children with known OSA experience opioid induced respiratory depression with greater incidence then in children without OSA.

Section D: Purpose and Objectives

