The sole objective in this study is to evaluate if routine amounts of opioids given for tonsillectomy in children have greater amounts of respiratory depression in children with documented obstructive sleep apnea when compared with patients that do not have obstructive sleep apnea

Section E: Protocol Risks/Subjects

E1. Risk Category

Category 3: Research involving greater than minimal risk and no prospect of direct benefit to the individual subject, but likely to yield generalizable knowledge about the subject's disorder or condition.

E2. Subjects

Gender:

Both

Age:

Child (3-12 yrs), Infant/Toddler (0-36 mos)

Ethnicity:

All Ethnicities

Primary Language:

English, Spanish

Groups to be recruited will include:

Asymptomatic patients with chronic conditions, healthy; Patients

Which if any of the following vulnerable populations will be recruited as subjects?

Children

Vulnerable populations require special protections. How will you obtain informed consent, protect subject confidentiality, and prevent undue coercion?

Parents will be approached as ask to participate in the study. They will be informed that this is completely voluntary and that they can choose to avoid participation and/or revoke their participation at any point. Their participation or lack thereof will not change or alter the care their child will receive. The risks include loss to confidentiality and we will reduce this risk by only having the PI and co-investigators collect data which will be stored only on the BCM firewall. Additionally, there is a risk of apnea with all opioids however this risk is routinely managed by pediatric anesthesiologists and encountered in nearly all anesthetics.

E3. Pregnant woman/fetus

Will pregnant women and/or fetuses (as described in 45 CFR 46 Subpart B) be enrolled in the research?

No

E4. Neonates

Will neonates of uncertain viability or nonviable neonates (as described in 45 CFR 46 Subpart B) be enrolled in the research?

No

E5. Children

Will children be enrolled in the research?

Yes

Section F: Design/Procedure

F1. Design

Select one category that most adequately describes your research:

c) Pilot

Discuss the research design including but not limited to such issues as: probability of group assignment, potential for subject to be randomized to placebo group, use of control subjects, etc.

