Endotracheal intubation using a RAE endotracheal tube will be performed with the size selected using the formula: Predicted Size Cuffed Tube = (Age / 4) + 3. Following endotracheal intubation, spontaneous ventilation will be maintained without the use of continuous positive pressure. Sevoflurane will be reduced to maintain between 0.5-0.7 MAC according to the Drager Apollo anesthesia machine. The patient will be allowed to establish their respiratory equilibrium for 3 minutes following intubation on 0.21% oxygen. Baseline tidal volume (TV), respiratory rate (RR) and end-tidal carbon dioxide (ETCO2) will be recorded. fentanyl 1mcg/kg will be administered as a bolus (usual clinical practice). The TV, RR, ETCO2 will be recorded, at 5 and 10 minutes After opioid administration. Apnea or desaturation (<92%) will be treated by assisting ventilation as required (standard practice). After 10 minutes,(to a repeated dose effect) a second dose of 1mcg/kg will be administered with the same TV, RR, ETCO2 recorded for 5 minutes.

Surgery will commence as usual with additional medication to be administered at the discretion of the anesthesiology providers. No change to standard practice will occur the research portion will be prospectively recorded the TV, RR, ETCO2 following opioid administration to calculate change from baseline (pre-opioid), routine fentanyl administration for these procedures is 2 mcg/kg

Section G: Sample Size/Data Analysis

G1. Sample Size

How many subjects (or specimens, or charts) will be used in this study?

Local: 50 Worldwide: 50

Please indicate why you chose the sample size proposed:

Our sample size is based on a recent 2019 landmark paper investigating a similar question in adults with obstructive sleep apnea we propose to enroll 20 control patients and 30 patients with documented obstructive sleep apnea

G2. Data Analysis

Provide a description of your plan for data analysis. State the types of comparisons you plan (e.g. comparison of means, comparison of proportions, regressions, analysis of variance). Which is the PRIMARY comparison/analysis? How will the analyses proposed relate to the primary purposes of your study?

The primary outcome will be measurement of continuous variables of tidal volume, respiratory rate and end tidal CO2. these will be reported as means with SD, regression analysis will be performed for patients falling into the moderate and severe categories of obstructive sleep apnea by sleep study.

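### No reading in the first 5 minutes after the first fentanyl bolus, and no log of apnea or assisted ventilation: a brief or treated early fall can be missed, and this is cheap to close

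*Combined protocol and SAP*

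**What the plan says.** Section F2 takes one pre-opioid reading after 3 minutes of equilibration: "Baseline tidal volume (TV), respiratory rate (RR) and end-tidal carbon dioxide (ETCO2) will be recorded". After the first bolus, "The TV, RR, ETCO2 will be recorded, at 5 and 10 minutes After opioid administration". The next sentence covers events: "Apnea or desaturation (<92%) will be treated by assisting ventilation as required (standard practice"). It gives no time window, and it does not ask for the event, its time or the assistance to be written down. At 10 minutes, "a second dose of 1mcg/kg will be administered with the same TV, RR, ETCO2 recorded for 5 minutes"; how often within those 5 minutes is not stated. The same procedure text is repeated in Sections H1 and H2.

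Section F2 says the readings are taken "following opioid administration to calculate change from baseline (pre-opioid"), without naming the time point. Section G2 adds: "The primary outcome will be measurement of continuous variables of tidal volume, respiratory rate and end tidal CO2". It names no time point, no worst value and no event component.

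The sole objective in Section D is whether there are "greater amounts of respiratory depression in children with documented obstructive sleep apnea" than in children without it. Section C puts the aim as whether children with OSA "experience opioid induced respiratory depression with greater incidence then in children without OSA".

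**The concern.** The trial asks how much ventilation falls after the opioid, and in Section C how often. For the first dose it looks at two moments. If tidal volume or rate drops and recovers between 0 and 5 minutes, neither reading shows the drop. If a child stops breathing at minute 2, is assisted and is breathing again by minute 5, the data sheet has no place for the event, and the 5-minute tidal volume and rate may look close to baseline.

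The first-dose response is the only one that starts from an opioid-free baseline. Minutes that were not recorded cannot be recovered at the analysis stage, so the gap has to be closed before data collection.

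**Working it through.** **Figures in the plan.** No stated figure tests this point. The only related arithmetic is the sample size, 20 + 30 = 50, which agrees. The documents give no time of peak effect, no standard deviation, no alpha and no power. What follows is illustration on assumed inputs.

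**1. Coverage, from the text alone.**
- First bolus: scheduled readings at 5 and 10 minutes; none from 0 to 5.
- Second bolus: recorded for 5 minutes, frequency not stated. This may cover the early minutes of that dose, but it starts 10 minutes after the first bolus, on top of residual drug.
- Apnea, desaturation and assistance: treated, not recorded, at any time.

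**2. How much of a fall the 5- and 10-minute readings show.** Assumed inputs: drug effect peaking at tp = 2, 3, 4 or 5 minutes; peak reduction in drive D = 40%, 60% or 80%; decay half-life 15 minutes; CO2 time constant T = 4 or 8 minutes; ventilatory slope 8% of baseline per mmHg; baseline CO2 40 mmHg. That gives 4 x 3 x 2 = 24 scenarios.
- Drug effect: e(t) = [exp(-kt) - exp(-at)], scaled to 1 at its peak, with k = ln 2 / 15 = 0.046 per minute and a chosen so that ln(a/k)/(a - k) = tp.
- Ventilation relative to baseline: V = (1 - D e(t)) x (1 + 0.08 (C - 40)).
- CO2: dC/dt = (40 - V C)/T.

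One scenario, tp = 3, D = 60%, T = 4: ventilation is lowest at 1.75 minutes, 40% below baseline. At 5 minutes the fall is 55% of that worst value and at 10 minutes 28%. CO2 peaks at 5.3 minutes, 10.2 mmHg above baseline, and the 5-minute reading is also 10.2 mmHg above.

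| Quantity | Range over 24 scenarios |
|---|---|
| Time of lowest ventilation | 1.0 to 4.0 min |
| Share of worst fall seen at 5 min | 37% to 96% |
| Share of worst fall seen at 10 min | 18% to 45% |
| Time of CO2 peak | 4.3 to 9.5 min |
| Share of peak CO2 rise seen by the larger of the two readings | 89% to 100% |

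The shape of the curve matters. If the drug effect rises in a straight line to its peak, ventilation is lowest at the peak itself (2 to 5 minutes), the 5-minute reading shows 36% to 100% of the worst fall, and the CO2 share is 84% to 100%. The model treats ventilation as a whole, does not split tidal volume from rate, and assumes unassisted breathing.

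**3. A curve without CO2 feedback.** With e(t) = (t/tp) exp(1 - t/tp), the larger of the 5- and 10-minute values as a share of the peak is:
- tp = 2: (5/2) exp(1 - 5/2) = 56%
- tp = 3: (5/3) exp(1 - 5/3) = 86%
- tp = 4: 97%
- tp = 5: 100%

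**4. What that would mean for power.** With 20 and 30 children, assumed two-sided alpha 0.05 and 80% power, the detectable difference is (1.960 + 0.842) x sqrt(1/20 + 1/30) = 2.802 x 0.2887 = 0.81 SD. If a true 0.81 SD difference at the peak shrank by the shares in step 3 and the SD did not change, power would be about 35% (tp = 2), 67% (tp = 3), 78% (tp = 4) and 80% (tp = 5). If the SD shrank as well, the loss would be smaller.

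**The case against.** The strongest case against this point has five parts.

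- **End-tidal CO2 is one of the three primary variables and lags ventilation.** In the same model that shows an early low point in ventilation, the scheduled readings catch 89% to 100% of the CO2 rise. This stands for unassisted breathing. A reader might infer that the deepest fall never enters the primary outcome; that is too strong. Assistance would tend to wash the CO2 signal out, so the protection is weakest in the children who were treated.
- **No passage says the effect peaks before 5 minutes.** This stands. The documents support only that a fall which peaks and recovers before 5 minutes is missed. The 2-to-5-minute peak is an assumption, and within it the loss runs from serious to trivial.
- **The second-bolus window may cover early minutes, and Section G2 does not tie the outcome to the first dose.** This stands in part: that window cannot give the first-dose response.
- **The apnea sentence is an undated contingency.** This stands. It does not show that the plan expects events between 0 and 5 minutes. The gap is in fact wider: apnea at any time is outside the primary outcome, and a reading taken during assistance has no rule.
- **The study is declared a pilot, and the choice of summary is a preference.** That bears on the weight of the point. It does not justify leaving out a recording that costs little and cannot be reconstructed.

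**Conclusion.** This is a cheap improvement to the plan and does not show that the primary comparison is invalid. From the text alone, a fall in tidal volume or rate that recovers or is treated before 5 minutes can go unseen for the first dose, and apnea and assistance are not recorded at all. The size depends on a peak time the documents do not give. Under the assumptions above, the 5-minute reading shows about 35% to 95% of the worst fall in ventilation, while the CO2 rise is largely caught.

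A reader might also infer that the OSA-control difference is pushed toward zero or reversed. The documents do not support that. With the same time course in both groups, the comparison at 5 minutes stays fair, though possibly of a smaller signal. A bias needs the groups to differ in when ventilation falls or when they are assisted. No passage says they do, and no group difference in timing was modelled.

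**What to change.** **Section F2 (and its repeats in H1 and H2).** Record tidal volume, respiratory rate and end-tidal CO2 each minute from the values the anesthesia machine already displays: minutes 1 to 10 after the first bolus and minutes 1 to 5 after the second. Log the time of any apnea, desaturation or assisted ventilation, and flag the assisted minutes. Minute readings alone are not enough, because an assisted breath would read as adequate ventilation.

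**Section G2.** Fix in advance one primary summary over minutes 1 to 10 after the first bolus, as change from baseline, for example the window mean. State how flagged minutes enter it. Keep the worst minute and the 5- and 10-minute values as secondary.

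**Cost.** 10 + 5 = 15 rows per child after the boluses, or 15 x 50 = 750 rows in all, plus an event log. It needs no new device, visit or patient and no change to dosing or care. A window mean dilutes a brief low point: in the 24 scenarios of the working it equals 46% to 75% of the worst fall. A worst-minute value avoids that but is noisier, which is why it is placed second.

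### F2 does not record whether a TV, RR or ETCO2 reading was taken during assisted ventilation, and G2 has neither a rule for such readings nor an event count; the resulting bias is of unknown size and direction

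*Combined protocol and SAP*

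**What the plan says.** **Baseline.** In F2 (Procedure), after intubation, "spontaneous ventilation will be maintained without the use of continuous positive pressure". Baseline TV, RR and ETCO2 are taken in that state after a 3-minute settling period.

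**Readings.** After the first fentanyl dose, "The TV, RR, ETCO2 will be recorded, at 5 and 10 minutes After opioid administration". Then "a second dose of 1mcg/kg will be administered with the same TV, RR, ETCO2 recorded for 5 minutes". The purpose given at the end of F2 is "to calculate change from baseline (pre-opioid)".

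**Assistance.** Between these recording instructions F2 states: "Apnea or desaturation (<92%) will be treated by assisting ventilation as required (standard practice)". The procedure text is repeated under H1 and H2 and adds nothing on this point.

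**Analysis.** In G2, "The primary outcome will be measurement of continuous variables of tidal volume, respiratory rate and end tidal CO2", and "these will be reported as means with SD", with a regression for the moderate and severe OSA categories.

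**Events.** E2 foresees the event: "there is a risk of apnea with all opioids however this risk is routinely managed by pediatric anesthesiologists". Yet in the visible text, which breaks off at H6, no outcome counts apnea, desaturation or assistance. Section D states the sole objective as the amount of respiratory depression. Section C states the aim as its incidence.

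**The concern.** Assisting ventilation acts directly on TV, RR and ETCO2. A reading taken during assistance reflects the provider as well as the child, whereas the baseline it is compared with reflects the child alone. The children who meet the trigger include those with the clearest depression, which is what the study sets out to compare.

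Two errors are possible. If assistance follows the depression and is commoner in OSA, altered readings would usually shrink the group difference. If assistance differs between groups for reasons other than the depth of depression, a difference can appear where none exists. Without a flag, the data that F2 names (TV, RR and ETCO2) cannot show which case applies or how many children are affected.

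**Working it through.** **1. The plan's own figures.** There is none to reproduce. G1 gives 20 controls and 30 children with OSA, citing an adult study, with no alpha, power, effect or SD. No assistance rate and no between-group test are given.

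**2. Where readings and assistance can coincide.** After dose 1 there are two reading times, 5 and 10 minutes; assistance may fall wholly between them. After dose 2, recording is for 5 minutes. Overlap is therefore possible at each stage but not certain. The rate that matters is the share of children assisted at the analysed reading, which can be lower than the share ever assisted.

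**3. Illustration; every input except 20 v 30 is assumed.** Take one generic fall from baseline, with SD s = 0.18, and a two-sided 5% t-test. A share p of the group is assisted at the reading. The trigger has correlation ρ with the fall, and an assisted reading shows a fall c. With z the normal quantile at 1−p and φ the normal density:

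- mean of all readings = (1−p)m − ρsφ(z) + pc
- mean of unassisted readings = m − ρsφ(z)/(1−p)

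For p = 0.05, φ(z) = 0.1031; for p = 0.20, φ(z) = 0.2800.

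**(A) True mean falls 30% v 45%, with 5% v 20% assisted.** The true difference is 15 points, with 81% power. For ρ = 1 and c = 0.15:

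- OSA: 0.80×0.45 − 0.18×0.2800 + 0.20×0.15 = 0.3396
- Control: 0.95×0.30 − 0.18×0.1031 + 0.05×0.15 = 0.2739
- Difference: 6.6 points

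Each further 15 points in c adds (0.20−0.05)×15 = 2.25 points. For unassisted readings only: (0.45 − 0.0504/0.80) − (0.30 − 0.0186/0.95) = 0.3870 − 0.2804, or 10.7 points. Simulation with 40,000 replicates agrees with these means to within 0.1 point and gives the power.

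| ρ | All readings, c = 15/30/45/60% (points) | Power | Unassisted only (power) |
|---|---|---|---|
| 1 | 6.6 / 8.8 / 11.1 / 13.3 | 29 / 56 / 74 / 80% | 10.7 (62%) |
| 0.5 | 8.2 / 10.4 / 12.7 / 14.9 | 33 / 58 / 75 / 81% | 12.8 (65%) |
| 0 | 9.8 / 12.0 / 14.3 / 16.5 | 40 / 65 / 81 / 87% | 15.0 (75%) |

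With 1% v 8% assisted, all readings give about 10.5 to 15.9 points over the same ranges. With 20% assisted in both groups, all readings give 0.80×15 = 12.0 points and unassisted readings 15.0.

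**(B) Equal true falls of 45%, with 5% v 20% assisted.** The expected difference is −0.15×0.45 − ρ×0.18×(0.2800−0.1031) + 0.15c = −0.0675 − 0.0318ρ + 0.15c. Rejection rates are in brackets.

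| ρ | All readings, c = 15% | All readings, c = 60% | Unassisted only |
|---|---|---|---|
| 1 | −7.7 (37%) | −0.9 (6%) | −4.3 (16%) |
| 0.5 | −6.1 (20%) | 0.7 (6%) | −2.2 (7%) |
| 0 | −4.5 (12%) | 2.25 (8%) | 0.0 (5%) |

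With equal falls and equal assistance rates the bias is 0.0 and rejection is 5%.

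**4. What (A) and (B) require.** At ρ = 1, (A) corresponds to nearly one common trigger: 0.30 + 1.645×0.18 = 0.596 in controls and 0.45 + 0.842×0.18 = 0.602 in OSA. (B) needs different triggers: 0.45 + 1.645×0.18 = 0.746 in controls against 0.602 in OSA. A false difference therefore needs assistance to differ between groups at the same depth of depression; masking does not.

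**5. Limit of the model.** ETCO2 would be expected to rise with hypoventilation, so a generic fall does not represent it.

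**The case against.** **Pooling is not ordered.** A reader might infer that the plan, followed as written, averages provider-delivered breaths. It does not say so. G2 is silent, and F2's requirement of spontaneous ventilation can be read as the condition for measurement. This stands: the text supports only that assisted readings could enter the means.

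**Overlap is not certain.** A reader might also infer that assisted readings are bound to occur. With two reading times after dose 1, assistance may miss both. This stands too.

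**The size is assumed.** It is tempting to take the low-power cells as the expected loss, or the −7.7 points as the expected false difference. Neither is supported. No input other than the group sizes comes from the documents, and the 60% column of (B) is close to zero.

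**The trigger is the same in both groups.** The sentence on attending preference concerns the anesthetic in general, so a false difference needs a further cause. This stands in part. The trigger includes SpO2, which is not an outcome, assistance is given at discretion, and the visible text describes no blinding of the provider to OSA status.

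**Dropping assisted readings is no cure.** At ρ = 1 in (A), unassisted readings give 10.7 points and 62% power. Averaging everything gives 11.1 to 13.3 points and 74–80% when assisted readings show falls of 45% or 60%. This stands and shapes the fix.

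**Section D is answerable.** Its sole objective concerns amounts, which continuous outcomes can address. A reader might infer that the lack of an event count defeats the study; it does not. Only Section C's incidence wording is left without a measure.

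**Pilot design and standard practice** explain the care given, not the missing flag. A pilot is well placed to learn how often assistance occurs.

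**Conclusion.** The gap is real and should be fixed. Readings used for change from an unassisted baseline may be taken during assistance. F2 does not mark them, and G2 neither says how to handle them nor counts the events. The effect on the OSA–control comparison could be masking or, under the further condition in step 4, a false difference.

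Its size is unknown. On the assumed inputs, a true 15-point difference appears as 6.6 to 16.5 points with 5% v 20% assisted, and an absent one as −7.7 to 2.25 points. These figures show what could happen, not what is likely, and they say nothing about ETCO2. The conclusion itself rests on the text of F2 and G2, not on the simulation. The documents do not say whether the clinical record would show assistance, so it cannot be claimed that the information is lost for good; it is only absent from the data the plan names.

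**What to change.** The care rule stays unchanged.

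1. **F2.** With each TV, RR and ETCO2 reading, record whether ventilation was assisted at that moment (yes/no). Per child, record any apnea, any SpO2 below 92% and any assistance in the observation window.
2. **G2.** Report the number assisted by group and time. Show mean change from baseline with SD both for all readings as recorded and for unassisted readings only. State that neither is unbiased when assistance tracks depression, and that both must be read with the counts.
3. **Supplementary descriptive outcome.** Report apnea, SpO2 below 92% or assisted ventilation by group, with risk difference and 95% CI. This also addresses Section C's incidence wording.

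A worst-rank composite, with assistance ranked worst, is optional. If it is used, state that with equal falls it can reject well above 5% when assistance rates differ for reasons unrelated to the fall: about 14% at 5% v 20% assisted and 22% at 10% v 30%.

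**Cost.** One field per reading, three per child, and a few sentences in F2 and G2. The binary outcome is imprecise at 20 v 30. Fisher power is about 19% for 5% v 20% and 34% for 10% v 30%. For example, 1/20 v 6/30 gives 20% − 5% = 15 points (Newcombe 95% CI −6 to 33). The protocol is listed as closed; if recording is finished, the flag could come only from clinical records, whose content the documents do not describe.

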Section H: Potential Risks/Discomforts

H1. Potential Risks

Describe any potential risks/discomforts; (physical, psychological, social, legal, or other) and assess the likelihood and seriousness of such risks:

Confidentiality and we will reduce this risk by only having the PI and co-investigators collect data which will be stored only on the BCM firewall.

Asymptomatic patients with chronic conditions, healthy; Patients

Children

Parents will be approached as ask to participate in the study. They will be informed that this is completely voluntary and that they can choose to avoid participation and/or revoke their participation at any point. Their participation or lack thereof will not change or alter the care their child will receive. The risks include loss to confidentiality and we will reduce this risk by only having the PI and co-investigators collect data which will be stored only on the BCM firewall.

Those with negative questionnaire scores will be included.

Study Group: Patients with Moderate to Severe OSA as documented by formal polysomnography For the study group, patients will be included if they have undergone formal sleep study evaluations. Stratification will be based on the polysomnography testing using the apnea hypopnea index (AHI) and/or the number desaturation events according to the McGill Scoring system for pediatric OSA. Patients with AHI greater than 6 will be considered to have moderate to severe OSA and thus eligible for inclusion

All patients will undergo general anesthesia per the usual practice at Texas Childrens Hospital according to the preferences of the anesthesiology attending physician. Induction will be sevoflurane/+nitrous oxide followed by intravenous access secured.

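### F2 and E2 say the research only records and care is unaltered, yet F2 fixes anaesthetic conditions and timing, and H1's risk text is incomplete

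*Combined protocol and SAP*

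**What the plan says.** **Usual care.** F2 says that all patients are anaesthetised in the hospital's usual way, as the attending prefers. After the measurement sequence it says: "No change to standard practice will occur the research portion will be prospectively recorded the TV, RR, ETCO2 following opioid administration". E2, in the field on consent and coercion, says of the children: "Their participation or lack thereof will not change or alter the care their child will receive". H1 and H2 repeat that sentence.

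**Fixed steps.** F2 also sets conditions for every child: spontaneous ventilation without continuous positive pressure, sevoflurane at 0.5-0.7 MAC, and "The patient will be allowed to establish their respiratory equilibrium for 3 minutes following intubation on 0.21% oxygen". A 1 mcg/kg fentanyl bolus follows, and "The TV, RR, ETCO2 will be recorded, at 5 and 10 minutes After opioid administration". Then: "After 10 minutes,(to a repeated dose effect) a second dose of 1mcg/kg will be administered", with 5 more minutes of recording.

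**Risk.** E1 selects "Category 3: Research involving greater than minimal risk and no prospect of direct benefit to the individual subject". E2 names loss of confidentiality and an apnea risk that it attributes to opioids in general. H1's own answer begins "Confidentiality and we will reduce this risk by only having the PI and co-investigators collect data" and continues with pasted text from E2 and F2.

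**The concern.** If the research portion is recording only, the attending decides gas level, ventilation and timing. If F2's specific steps govern, the study decides them. The protocol says both and does not mark which steps belong to the study.

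This matters in two ways. First, those who judge the risk to children cannot see what participation adds: E1 puts the study above minimal risk, while the recording-only description identifies no added procedure that would account for it.

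Second, tidal volume, respiratory rate and end-tidal CO2 are the primary outcome in G2, and F2 analyses them as change from a pre-opioid baseline. They respond to anaesthetic depth, ventilatory support and stimulation as well as to fentanyl. F2 expects some children to need assisted ventilation, yet neither F2 nor G2 says how a reading taken under assistance, or otherwise off the set conditions, is handled. If assistance is commoner in one group, the comparison between children with and without sleep apnea could be biased as well as less precise.

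**Working it through.** **1. Length of the sequence.** The documents give no total, so there is no stated figure to reproduce. Adding the F2 intervals:

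- equilibration before baseline: 3 min
- first bolus to second bolus: 10 min
- recording after the second bolus: 5 min
- total: 3 + 10 + 5 = 18 min from intubation to last reading, of which 10 + 5 = 15 min follow the first bolus; the second bolus falls at 3 + 10 = 13 min.

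This sum is nominal. F2 allots no time to recording the baseline.

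**2. Dose.** 1 + 1 = 2 mcg/kg, equal to the total that F2 calls routine. The total is therefore not shown to be research-driven; only the split and the timing could be. Section D's objective concerns routine amounts of opioid, so the readings after the second bolus are the only ones taken at the full routine amount.

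**3. Which steps the document itself calls usual.**

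- First 1 mcg/kg bolus: labelled usual practice.
- Assisted ventilation for apnea or desaturation: labelled standard practice.
- Second bolus and its timing: given a measurement reason (a repeated-dose effect), with no usual-practice label.
- MAC range, ventilation mode, 3-minute wait and oxygen level: no individual label.

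Usual practice for gas level, ventilation mode, dose interval or start of surgery is not described. The departure from it cannot be calculated.

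**4. Risk text side by side.**

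- E1: above minimal risk, no direct benefit.
- E2: confidentiality, plus apnea as a general opioid risk.
- H1, own words: confidentiality only. Its copy of the E2 paragraph stops just before the apnea sentence. Apnea and desaturation appear only in the pasted procedure, as events to be treated.
- H1 asks for likelihood and seriousness; neither is given.
- No section lists the observation period or the set conditions as something participation may add.

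**5. Oxygen figure.** As a fraction, 0.21 = 21%. Then 21% / 0.21% = 100. The figure stands in F2 and in the pasted text under H1 and H2.

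**6. What lost readings would cost (illustration).** G1 gives no alpha, power or SD. Assume two-sided 5%, 80% power and a normal approximation. The detectable difference in SD units is (1.960 + 0.842) × √(1/n₁ + 1/n₂).

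- 20 vs 30: 2.802 × √(1/20 + 1/30) = 0.81
- 10% of readings unusable in both groups (18 vs 27): 0.85
- 20% (16 vs 24): 0.90
- 30% (14 vs 21): 0.97

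**The case against.** The best defence is that the statements can be read together. Usual practice is never defined, so every fixed step might already be usual at this hospital. F2 labels the first bolus and the rescue as usual, and the total dose equals the stated routine total. Specific steps ordinarily govern over a general clause about preference. This stands to the extent that the documents do not prove a departure from usual practice. It does not remove the conflict over who decides the conditions, and it leaves the measurement reason for the second bolus at odds with a recording-only study.

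Stronger readings are tempting, and the documents do not support them:

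- **That the statements cannot all be true, or that a child spends up to 18 extra minutes under anaesthesia.** Without a description of usual practice, neither follows. Eighteen minutes is the nominal length of the sequence, not a measure or a limit of added time.
- **That the risk statement is wrong.** E1 already says above minimal risk and E2 names apnea. The text is incomplete and inconsistent.
- **That surgery will contaminate the last readings.** F2 places the start of surgery after the final recording, and the discretion stated there concerns additional medication. Overlap is possible but conjectural.
- **That parents consent on a false statement, so the E2 sentence should go.** The consent form is not available here. The sentence answers a question about coercion and also serves as an assurance that refusal carries no penalty, which deletion would remove.

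**Conclusion.** The concern holds as an internal inconsistency that should be corrected. F2 and E2 describe a study that only records and leaves care unaltered. F2 then sets gas level, ventilation mode, oxygen level and a timed two-bolus sequence of nominally 18 minutes, without saying which of these the study imposes. H1 does not complete the risk account that E1 and E2 begin. The oxygen figure is ambiguous by a factor of 100 in an operative instruction.

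The size of any departure from usual care is unknown. The effect on the results is also unknown, because the frequency of assisted ventilation or early stimulation is not given. The precision figures in the working rest on assumed alpha and power, and they do not capture bias. The conclusion depends on none of these: it rests on the wording of E1, E2, F2 and H1. No position is taken on which dose, gas level, oxygen level or ventilation rule is right.

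**What to change.** - **Reconcile E1, E2, F2 and H1.** State step by step what the study fixes and what is left to the attending. Correct the no-change and care-unaltered sentences to match rather than simply deleting them, and keep the assurance that refusal carries no penalty.
- **Complete H1.** Name apnea, desaturation and the study observation period, each with likelihood and seriousness.
- **Reconcile the oxygen figure** in F2 and in the copies under H1 and H2.
- **Record clock times** of intubation, both boluses, each reading and first surgical stimulation.
- **Flag readings** taken after stimulation begins or under assisted ventilation. Report how many there are in each group, and report change from baseline by group with and without them. Exclusion alone would not do: assistance may be a response to the respiratory depression under study, so dropping those readings could itself bias the comparison.

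The cost is a wording amendment, a few extra times per child and one small sensitivity analysis. The protocol is marked closed, so the wording changes may now serve mainly the record; the handling of flagged readings still matters for analysis and reporting.
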